Data presented in table 1 will be used to describe patient characteristics by randomisation group at baseline. Categorical variables will be presented with numbers and percentages. Means and standard deviations will be reported for normally distributed continuous variables; medians, interquartile ranges, and ranges will be reported for skewed data. Tests of statistical significance will not be performed for baseline characteristics. Because the groups arise from a non-randomised study design, standardised differences will be used to assess between-group imbalances, with attention to differences of potential clinical importance.

ANALYSIS

Outcome and endpoint definitions

Primary:

Outcome:

The primary outcome of this trial is the patient's perceived symptom acceptability in relation to their upper extremity condition, measured using the concept of the Patient Acceptable Symptom State (PASS). PASS was originally designed for rheumatic disorders,²⁸ but has shown to be a useful outcome for other musculoskeletal and orthopaedic conditions.²⁹⁻³² The PASS defines the highest level of symptom at which patients find their condition acceptable.³³

Endpoint:

The primary endpoint is the proportion of participants responding "Yes" to the PASS anchor question:

"Taking into account all your daily activities, pain and functional impairment, do you consider your current state satisfactory?"

This binary endpoint (Yes/No) will be assessed at 1 year post allocation. A higher proportion of "Yes" responses indicates a more favourable outcome in symptom acceptability.

Co-Primary:

Outcome:

The co-primary outcome of this trial is the change in upper extremity disability, assessed using the Quick Disabilities of the Arm, Shoulder and Hand (Quick-DASH) questionnaire.³⁴ The Quick-DASH is a validated, patient-reported measure designed to evaluate physical function and symptoms in people with musculoskeletal disorders of the upper limb.^{34,35} A relative change exceeding 41% has been proposed as a clinically meaningful threshold for improvement in upper extremity conditions.³⁵

Endpoint:

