The co-primary endpoint is the proportion of participants achieving a reduction greater than 41%, corresponding to a minimal important change,³⁵ in their Quick-DASH score from baseline to 1 year post allocation (Quick-DASH MIC). This binary endpoint (achieved/not achieved) reflects whether an individual's improvement surpasses the defined clinically important change. A higher proportion of patients reaching this threshold indicates a more favourable treatment effect on physical function and symptoms.

Key Secondary:

The following key secondary outcomes will be analysed to assess the between-group differences in treatment effects over time. Unless otherwise stated, the primary analysis time point for all key secondary outcomes is 1 year after treatment allocation. Additional measurements will be taken at 3 and 6 months for descriptive and exploratory analyses of trajectories over time.

1. Global Perceived Effect (GPE)

Outcome:

Patient-reported global impression of change in "Overall shoulder problems", measured using a 15-point Likert scale ranging from "A great deal worse" (score = 1) to "A great deal better" (score = 15).

Endpoint:

The participants answer on the GPE question “All in all, how do you experience your shoulder problems now compared to before you started your treatment in the study?” will be dichotomised into “Improved” (score > 9) and “Not improved” (score ≤ 9). The key secondary endpoint is the proportion of participants classified as “Improved” at 1 year after treatment allocation. The GPE has been shown to be a valid and reliable outcome measure in shoulder trials and is recommended by OARSI.^{36 37}

2. QuickDASH Score

Outcome:

Self-reported upper extremity disability and symptom severity, measured using the 11-item Quick Disabilities of the Arm, Shoulder and Hand (QuickDASH) questionnaire.³⁴ Each item is rated on a 5-point Likert scale and transformed into a total score ranging from 0 (no disability/symptoms) to 100 (most severe disability/symptoms). The optional work and sports/music modules are excluded from the analysis. The QuickDASH has demonstrated high reliability, validity, and responsiveness in patients with shoulder conditions.^{34 35}

Endpoint:

The key secondary endpoint is the between-group difference in change in total QuickDASH score from allocation to 1 year follow-up. The outcome will also be measured at 3 and 6 months for secondary analyses.

3. Shoulder Pain Intensity variables

Outcome:

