Pain intensity in the affected shoulder over the past 7 days, assessed separately in three specific contexts:

- Maximum pain experienced
- Pain during physical activity
- Pain at rest

Endpoint:

Each pain domain is measured on a 100 mm visual analogue scale (VAS) anchored with 0 = “No pain” and 100 = “Worst pain imaginable,” as recommended by the OARSI.³⁶ The key secondary endpoint is the between-group difference in change from allocation to 1 year follow-up. Additional measurements will be collected at 3 and 6 months.

4. Shoulder-Related Sleep Disturbance

Outcome:

Degree of sleep disturbance attributed to shoulder symptoms in the past 7 days.

Endpoint:

Measured using a 100 mm VAS, anchored with 0 = “Not disturbed” and 100 = “Extremely disturbed.” The key secondary endpoint is the between-group difference in change from allocation to 1 year follow-up, with additional measurements at 3 and 6 months.

Covariates for development of propensity score

To account for potential confounding and to improve comparability between the surgical and non-surgical treatment cohorts, propensity score adjustment will be applied. The propensity

score will be estimated as the conditional probability of receiving surgical treatment, given a set of baseline covariates measured prior to treatment allocation.

Covariates are selected based on clinical relevance and their potential association with both treatment assignment and outcomes. These include patient-reported measures of general health, health-related quality of life, fear-avoidance beliefs, treatment expectations, and physical activity levels, as well as sociodemographic characteristics (e.g., age, sex, education), lifestyle factors (e.g., smoking, BMI), and clinical assessments including imaging and physical examination findings.

All covariates used in the propensity score model were collected prior to referral to either surgical or non-surgical treatment pathways. The full list of covariates and the timing of their assessment, along with the timing of primary and secondary outcome measurements, is detailed in Box 1.

Box 1: Outcome and Covariates – Timepoint of assessment.

	Timepoint of assessment			
	Baseline	3 months	6 months	1 year
Outcome measures				
Primary outcome				
PASS, no. (%)				X
Quick-DASH MIC, no. (%)				x
Key Secondary Outcomes				
GPE - Overall shoulder problems - no. (%)				X
Quick-DASH - 0-100	X	X	X	X
VAS shoulder pain 'Maximum' - 0-100	X	X	X	X
VAS shoulder pain 'Activity' - 0-100	X	X	X	X

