VAS shoulder pain 'Rest' - 0-100	X	X	X	X
VAS shoulder related sleep disturbance - 0-100	X	X	X	X
Covariates (de-confounding variables)				
Demographic variables				
Age (years)	X			
Female sex, no. (%)	X			
Body Weight (kg)	X			
Height (cm)	X			
BMI (kg/m ²)	X			
Central adiposity (Waist-To-Height ratio > 0.50), no. (%)	X			

Marital status	X			
- Married or cohabitating, no. (%)				
Educational level	X			
- Education above high school level, no. (%)				
Work status	X			
- Employed for wages or Self-employed, no. (%)				
- Unemployed, no. (%)				
- Sick-leave, no. (%)				
- Retired, no. (%)				
- Other, no. (%)				
Smoking status	X			
- Current smoker, no. (%)				
- Previous smoker, no. (%)				
- Non-smoker, no. (%)				
Alcohol consumption	X			
- >7 units/week, no. (%)				
Multiple Pain sites	X			
- 0 pain sites (besides current shoulder pain), no. (%)				
- 1-2 pain sites (besides current shoulder pain), no. (%)				
- >2 pain sites (besides current shoulder pain), no. (%)				
Comorbidity, no. (%)	X			
- No comorbidities, no. (%)				
- 1-2 comorbidities, no. (%)				
- >2 comorbidities, no. (%)				
Preference regarding treatment	X			
- Surgery, no. (%)				
- Corticoid injection, no. (%)				
- Physiotherapy, no. (%)				
- Other, no. (%)				
Expectation of treatment effect – 0 (No effect) – 100 (Complete recovery)	X			
Treatment received prior to referral due to current shoulder pain	X			
- None, no. (%)				
- Physiotherapy or Chiropractor treatment, no. (%)				
- Corticoid injection, no. (%)				
Current workers compensation claim, no. (%)	X			
Current insurance compensation claim, no. (%)	x			
Sick leave due to shoulder within the last 3 months – days	X			
Clinical assessment variables				
Duration of current shoulder pain	X			
- <3 months, no. (%)				
- 3-6 months, no. (%)				
- >6-12 months, no. (%)				
- >12 months, no. (%)				
Presence of constant pain, no. (%)	X			
Injury history	X			
- Traumatic, no. (%)				

- Acute overuse (Short duration of hard work, without history of trauma), no. (%)				
- Prolonged overuse (Prolonged stress on shoulder), no. (%)				
- Unknown, no. (%)				
Use of analgesics due to shoulder-related pain	X			
Use of analgesics not due to shoulder-related pain	X			
Taking medication due to Hypertension, no. (%)	X			
Taking medication due to Elevated serum triglycerides or Low serum high-density lipoprotein (HDL) , no. (%)	X			
Insulin resistance, no. (%)	X			
Metabolic syndrome*, no. (%)	X			

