The primary analyses will be based on the Intention to Treat (ITT) population. Categorical endpoints (e.g., the proportion achieving PASS/Quick-DASH MIC after 1 year) will be analysed using logistic regression, with treatment group and stratification factors as covariates, based on the IPW data provided initially. The primary estimand will be the odds ratio (OR) with 95% confidence intervals (CIs) derived from the fully adjusted logistic regression model. The main analysis will use inverse probability weighting, with further adjustment for stratification variables. The OR will represent the treatment effect, with CIs providing the range within which the true treatment effect is expected to lie with 95% certainty. A p-value will be reported to assess the statistical significance of the treatment effect, testing the null hypothesis of no difference between groups. An OR >1 indicates higher odds of achieving the PASS/Quick-DASH MIC outcome with surgical treatment, while an OR <1 indicates lower odds. For secondary objectives, categorical outcomes will be analysed using the same approach as the primary endpoints, while continuous outcomes will be analysed as change from baseline using repeated-measures mixed-effects linear models. Patient identification number will be included as a random effect. Fixed effect factors will include baseline score, treatment group (Shoulder Surgery vs Nonoperative Treatment), time point (baseline, 3, 6, and 12 months), stabilised inverse probability of treatment weighting (sIPTW), and treatment-by-time interactions.

Sensitivity analysis will be performed with the purpose to test the robustness of the primary analyses, based on the per-protocol population, if $>5\%$ of the total number of patients in one treatment group are major protocol violators. The per-protocol analysis set will include: 1) patients who in the surgical group were 'allocated (initial clinical decision at first medical examination) to receive surgery, and have a record of the surgery was performed in the REDCap database, including date and type of surgery performed, 2) patient who in the non-surgical group were allocated (initial clinical decision at first medical examination) to receive non-surgical treatment and a minimum of 1 record, in the REDCap database, of receiving non-surgical intervention after the initial clinical examination as well as no record of surgery performed.

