Morphine or opioids — no. (%)

Other — no. (%)

Diagnostic group

Degenerative — no. (%)

Non-Specific shoulder pain — no. (%)

Non-traumatic instability/luxation — no. (%)

Traumatic injury — no. (%)

Quick-DASH score‡ — 0 to 100

VAS Shoulder pain Maximum§ — 0 to 100

VAS Shoulder pain Activity§ — 0 to 100

VAS Shoulder pain Rest§ — 0 to 100

VAS Shoulder related sleep

Disturbance§ — 0 to 100

* Plus-minus values are mean \pm SD unless otherwise indicated.† The Danish Health Authority guideline recommends alcohol consumption lower than 7 units per week for females and 14 units per week for males to have a low risk of developing diseases.⁴⁸

‡ The short version of the Disability of the Arm, Shoulder and Hand Questionnaire (Quick-DASH) ranges from 0 to 100, with higher scores indicating worse disease status.

§ Visual Analog Scale (VAS) ranges from 0 to 100, with higher scores indicating worse status.

Table 2. Primary and Key Secondary Outcomes at 1 year in the Intention-to-Treat Population.*

VARIABLE	SURGICAL GROUP	NON-SURGICAL GROUP		BETWEEN GROUP	
		OR (95%CI)		Crude	Adj.
PRIMARY OUTCOME					
PASS - no. (%)					
QUICK-DASH MIC - no. (%)					
KEY SECONDARY OUTCOME					
GPE - OVERALL SHOULDER PROBLEMS - no. (%)					

	Mean change from baseline	SE	Mean change from baseline	SE	LSMean difference (95% CI)	
					Adj.	p-value
Quick-DASH - 0 to 100						
VAS SHOULDER PAIN MAXIMUM - 0 to 100						
VAS SHOULDER PAIN ACTIVITY - 0 to 100						
VAS SHOULDER PAIN REST - 0 to 100						
VAS SLEEP DISTURBANCE - 0 to 100						

PASS: Patient Acceptable Symptom State; GPE: Global Perceived Effect; Quick-DASH: Short form of Disability of the Arm, Shoulder and Hand questionnaire; VAS: Visual Analog Scale. * All analyses will be based on the ITT population: For dichotomous outcomes, logistic regression will be applied, with treatment group and stratification factors as covariates, based on the IPW data (missing data at 1 year from allocation will be addressed through non-responder imputation); The primary estimate will be the odds ratio (OR) with 95% confidence intervals (CIs) derived from the logistic regression model. For continuous outcomes, repeated measures linear mixed effects models (with no imputation for missing data) will be applied; Estimates are mean change from baseline and standard deviations with difference between groups reported with 95% confidence intervals.

Figures:

[figure not shown]

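### Baseline Quick-DASH, pain VAS and sleep VAS enter neither the propensity model nor the weighted logistic models, so PASS, Quick-DASH MIC and GPE are not adjusted for them

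*SAP*

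**What the plan says.** The section *Covariates for development of propensity score* sets the selection rule: "Covariates are selected based on clinical relevance and their potential association with both treatment assignment and outcomes". It then refers to Box 1 for the list: "The full list of covariates and the timing of their assessment, along with the timing of primary and secondary outcome measurements". Box 1 has an outcome block, followed by a block headed "Covariates (de-confounding variables". Quick-DASH, the three pain VAS (maximum, activity, rest) and the sleep VAS carry a baseline mark, but only in the outcome block. The patient-reported measures in the covariate block are WHO-5, EQ VAS, PSEQ(4), TSK-13 and UCLA-as.

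Under *Analysis methods*, categorical endpoints "will be analysed using logistic regression, with treatment group and stratification factors as covariates", on the weighted data. The Table 2 footnote says the same: "logistic regression will be applied, with treatment group and stratification factors as covariates, based on the IPW data". GPE follows the approach of the primary endpoints. The mixed models for the continuous secondary outcomes differ: "Fixed effect factors will include baseline score, treatment group" and further terms.

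The co-primary endpoint is relative to baseline: "The co-primary endpoint is the proportion of participants achieving a reduction greater than 41" per cent in Quick-DASH at one year. Table 1 lists all five scores, and under *Baseline patient characteristics* "standardised differences will be used to assess between-group imbalances".

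**The concern.** In this emulated trial, the causal reading of the odds ratios depends on the measured confounders being balanced after weighting. How disabled, painful and sleep-disturbed a patient is at presentation plausibly affects both the decision to operate and the state one year later. The five scores therefore plausibly meet the SAP's own selection rule. The PASS question itself asks about daily activities, pain and functional impairment, which is largely what Quick-DASH and the pain VAS measure. For Quick-DASH MIC the link is closer still, because the baseline score is the denominator of the endpoint.

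If the scores stay unbalanced after weighting, neither model corrects this. Table 1 may show the imbalance, but the plan provides no adjustment, so any correction would be made after the data are seen.

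**Working it through.** **1. Are the scores in either model?** Counting the covariate block of Box 1 gives 19 demographic + 29 clinical + 5 patient-reported = 53 items, none of which is one of the five scores. The outcome model holds treatment group and stratification factors. The stratification factor is diagnostic group (*Trial design*), which is not a severity score. *Analysis methods* also calls the model fully adjusted, but the next sentence defines the adjustment as weighting plus stratification variables. The scores are in neither model.

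**2. How crowded is the propensity model?** If each multi-category item is dummy-coded as a single choice (my assumption), the parameters are 28 + 46 + 5 = 79. At 1:15 and N = 992 (*Sample size and power considerations*), the surgical group is 992/16 = 62 and the non-surgical group 930.

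**3. What could a residual imbalance do?** The SAP gives no figure for this, so the calculation is illustrative.

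- From the SAP: 60% success in the non-surgical group (planning value).
- Assumed: no true treatment effect; one standardised score x, distributed N(0,1) in the non-surgical group and N(d,1) in the surgical group after weighting; an odds ratio r for success per SD of x.
- Formula: logit p(x) = a + ln(r)·x, with a solved so that the mean of p(x) over N(0,1) is 0.60. The surgical proportion p1 is the mean of p(x) over N(d,1). The estimated odds ratio is [p1/(1 − p1)] / (0.60/0.40).

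For PASS, a higher score means worse status, so r is below 1:

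| d (SD) | r per SD | a | p1 | Estimated OR |
|---|---|---|---|---|
| 0.1 | 0.80 | 0.410 | 59.5% | 0.98 |
| 0.3 | 0.65 | 0.423 | 57.0% | 0.88 |
| 0.5 | 0.50 | 0.449 | 52.3% | 0.73 |
| −0.1 | 0.80 | 0.410 | 60.5% | 1.02 |
| −0.3 | 0.65 | 0.423 | 62.9% | 1.13 |
| −0.5 | 0.50 | 0.449 | 67.3% | 1.37 |

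Positive d means the surgical group is worse at baseline.

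For Quick-DASH MIC the direction of the baseline effect is unknown, so r is taken from 0.8 to 1.25, again with 60% success. At d = 0.1 the odds ratio is 0.98 or 1.02. At d = 0.5 it is 0.90 or 1.12.

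**4. How large is this against sampling error?** The unweighted standard error of ln(OR) at 60% in both groups is √[1/(62 × 0.24) + 1/(930 × 0.24)] = 0.268. For PASS with the surgical group worse, the shift is |ln 0.978|/0.268 = 0.08 standard errors in the smallest case, |ln 0.884|/0.268 = 0.46 in the middle case and |ln 0.731|/0.268 = 1.17 in the largest.

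**The case against.** The strongest reply is that much of the route from severity to allocation is already covered. Box 1 contains treatment preference, expected effect, constant pain, symptom duration, analgesic use, sick leave due to the shoulder, range of motion, strength, cuff rupture, EQ VAS and PSEQ. Only the part of each score that these items do not explain can bias the result, so the upper end of the assumed range may be too high. With 0.1 to 0.2 SD and an odds ratio of 0.8 to 0.65 per SD, the estimate is 0.98 to 0.92, or 0.08 to 0.31 standard errors. This stands as a limit on size. It does not show that the proxies balance the scores, and the direct measures are already collected.

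It can also be said that the contrast with the mixed models is unfair to PASS and GPE, which are recorded only at one year and have no baseline value of their own. That is correct: as an own-baseline contrast, the point applies only to Quick-DASH MIC. The confounding argument for PASS and GPE does not depend on it.

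Finally, a model with about 79 parameters and 62 surgical patients may not balance anything added to it. This is a real constraint. It argues for choosing covariates by importance, and a list that keeps redundant items while leaving out baseline shoulder severity does not do so.

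**Conclusion.** The point holds. Followed as written, the SAP leaves baseline Quick-DASH, the three pain VAS and the sleep VAS unadjusted in both primary comparisons and in GPE. That much follows from the text with high confidence.

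The consequence is less certain. Diagnostic group and many indirect severity markers are adjusted for, so only imbalance left after weighting matters, and the SAP does not allow its size or direction to be derived. Under the stated assumptions the effect on PASS runs from negligible to more than one standard error. For Quick-DASH MIC the assumed range is narrower, 0.90 to 1.12. This should be fixed: the effect may be small, but the bias is avoidable with data already in hand.

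**What to change.** Before data extraction:

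- Add baseline Quick-DASH and baseline maximum pain to the covariate block of Box 1, and the sleep VAS if the model supports it.
- Make room by dropping weight and height (BMI is listed) and metabolic syndrome (its components are listed). This frees three parameters for the two or three added: 79 − 3 + 2 = 78, or 79 with the sleep VAS.
- Report weighted standardised differences for Quick-DASH, all four VAS scores and diagnostic group.
- Optionally, add baseline Quick-DASH to the weighted logistic models for PASS, Quick-DASH MIC and GPE, and state that this changes the conditional odds ratio being estimated.

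If extraction has already begun, the change should be dated and labelled as made after publication of the SAP.

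The cost is small, since all five scores are collected and already appear in Table 1. The swap leaves the model about as crowded as before and does not cure that problem. Adding the scores without pruning would strain it further and risk extreme weights.

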In this pragmatic emulation of a stratified, randomised, open-label, superiority trial, adults referred to secondary care with various shoulder diagnoses and medical imagine verified pathology were initially allocated into either Surgery group, or the Non-Surgical Treatment group with an expected allocation ratio of 1:15. The primary endpoint in the intention-to-treat population was PASS assessed one year from allocation of treatment. Secondary endpoints was assessed also at 3 and 6 months after allocation of treatment. We will analyse observational data from the prognostic Vejle Hospital Shoulder Cohort (VHS Cohort), initiated to evaluate prognostic factors for consistent pain 1 year after diagnosis, using a “causal inference framework”, in an attempt to emulate a randomised target trial, stratified per diagnostic group defined as 1) Degenerative; 2) Traumatic injury; 3) Non-traumatic instability/luxation; 4) Non-specific pain, based upon ICD-10 diagnosis and traumatic/non-traumatic anamnesis (Illustration 1), that would answer the question whether more patients referred for surgery based on a surgeon’s clinical evaluation will reach a satisfactory outcome, when compared to patients not referred for surgery. Thus, causal inference from these observational data needs to be evaluated with respect to how well they emulate a particular target trial that is not feasible/ethical to perform.

[figure not shown]

Illustration 1: Diagnostic grouping based on ICD-10 diagnoses.

The statistical analysis plan (SAP) is reported in accordance with the “Guidelines for the Content of Statistical Analysis Plans in Clinical Trials”.²⁴ Reporting of the trial will follow the “Consolidated Standards of Reporting Trials” (CONSORT).^{25 26}

The trial was registered at Clinicaltrials.gov (NCT04686435) in 12/2020. First patient was enrolled in January 2021. Last patient last follow-up was January 2025. The trial has been evaluated and approved by The Regional Committees on Health Research Ethics for Southern Denmark (Project.ID: S-20202000-16) and the Danish Data Protection Agency (journal no: 20/12316).

Group allocation

Allocation to surgery or non-surgical treatment is based on the clinician’s initial overall judgment, taking into account patient history, clinical examination, imaging findings, patient expectations, relevant clinical guidelines and shared decision making. This real-world allocation process was analytically emulated to reflect a trial-like comparison.

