Sample size and power considerations

The sample size calculation applies jointly to both primary efficacy objectives. A power analysis for comparing two proportions using Pearson’s chi-square test indicated that, with a 1:15 allocation ratio between groups, a total sample size of 992 would provide 92% power to detect a 20 percentage point absolute difference (0.80 vs. 0.60) at a two-sided significance level of 5% ($\alpha = 0.05$). The calculation employed a normal approximation to the binomial distribution under the null hypothesis of no difference in proportions. For practical and operational considerations, the sample size was rounded up to 1000 participants to ensure sufficient power and account for potential deviations.

Framework

Both primary and secondary outcomes are analysed within a superiority framework; surgical interventions are favourable compared to non-surgical interventions.

Statistical interim analysis and stopping guidance

No statistical interim analysis is planned on the primary endpoint.

Timing of final analysis

Data extraction and analysis for the between-group comparison (Surgical vs. Non-Surgical) for the primary endpoint (1 year follow-up) is planned to be performed after making this SAP public available. The main publication of the trial will be prepared when these data have been received and cleaned (anticipated by September 2025).

Timing of outcome assessments

The overview of trial procedures and time-point of each outcome assessment is presented in the **Illustration 2** “Timeline for recruitment and follow-up” and **Box 1** “Outcomes and Covariates – Timepoint of assessment”. The Treatment allocation date (Surgical or Non-surgical) is used to calculate 3 months, 6 months and 1 year follow-up time points.

[figure not shown]

Illustration 2: Timeline for recruitment and follow-up. -t₂: 2-4 days prior to medical examination; -t₁=Day of medical examination; t₀=Allocation; t₁= 3 months; t₂= 6 months; t₃= 1 year.

STATISTICAL PRINCIPLES

Confidence intervals and p-values

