To analyse observational data for causal treatment effects, the most important methodological challenge is to control bias due to lack of randomisation. With the rising challenge of analysing more complex observational data, the propensity score has been the foundation for many of these approaches. Bias control methods based on propensity scores have become widely accepted. To define the propensity score, we introduce the following notation: let $X = (X_1, \dots, X_n)$ represent n confounders that are measured prior to intervention initiation (referred as “baseline confounders” below), then $X_i = (X_{1i}, \dots, X_{ni})$ is a vector of the value of the n confounders for the i^{th} subject. Let T represent the available interventions, with $T = 1$ indicating the subject is in the group initially allocated to surgery and $T = 0$ meaning the subject in the control group (ie, referral to non-surgical intervention). For the i^{th} subject, the propensity score is the conditional probability of being in the treated group given their measured baseline confounders,

$$\text{Prob } (X_i) = (T_i = 1 \mid X_i)$$

Intuitively, the propensity score provides a way to simulate randomisation when actual randomisation is not feasible. By conditioning on the propensity score, we aim to ensure that each subject has an equal chance of receiving treatment, thereby balancing the distributions of measured baseline confounders between treatment and control groups. The stabilized inverse probability treatment weighting (sIPTW) approach will be used as the analysis. A multivariable binomial logistic regression model will be utilised to generate the propensity scores.

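### At the planned 1:15 ratio about 62 surgical patients must support a propensity model of about 75–79 coefficients, and no variance estimator is named, so error control of the primary PASS test is undetermined

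*SAP*

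**What the plan says.** Trial design describes two groups "with an expected allocation ratio of 1:15". Sample size and power considerations states that "a total sample size of 992 would provide 92% power to detect a 20 percentage point absolute difference", using an unweighted Pearson chi-square test at 0.80 against 0.60, and rounds the total up to 1000.

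Covariates for development of propensity score refers to Box 1 for "The full list of covariates and the timing of their assessment". Analysis methods then fixes the model ("A multivariable binomial logistic regression model will be utilised to generate the propensity scores") and the weights: "The stabilized inverse probability treatment weighting (sIPTW) approach will be used as the analysis". For the binary endpoints, "The main analysis will use inverse probability weighting, with further adjustment for stratification variables". The odds ratio, its 95% confidence interval and the p-value all come from that weighted logistic regression. How its variance is estimated is not stated.

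Two descriptive items bear on the point. Under Baseline patient characteristics, "standardised differences will be used to assess between-group imbalances", but the Table 1 shell has no weighted column and no threshold or action is attached. Table 2 sets a crude odds ratio beside the adjusted one. The only sensitivity analysis is per-protocol, and no additional analyses are planned.

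**The concern.** A logistic propensity model with more coefficients than patients in the smaller arm overfits. It assigns some surgical patients a very low fitted probability of surgery, and hence a very large weight. Stabilisation does not help here. It multiplies every weight in an arm by one constant, so the relative weights within the surgical arm are unchanged.

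The result can rest on a handful of surgical patients while the reported interval does not reflect that. PASS is the first step of the hierarchy under Confidence intervals and p-values, so a false rejection there opens testing of the later outcomes. Because no variance estimator is named, two analysts following the SAP faithfully could report very different p-values from the same data.

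**Working it through.** **1. The SAP's own power.** Inputs from Sample size and power considerations: 62 surgical and 930 non-surgical patients, 0.80 against 0.60, two-sided 5%.

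- Pooled rate: (0.80×62 + 0.60×930)/992 = 0.6125.
- SE under the null: √[0.6125×0.3875×(1/62 + 1/930)] = 0.0639.
- SE under the alternative: √[0.80×0.20/62 + 0.60×0.40/930] = 0.0533.
- Power: Φ[(0.20 − 1.96×0.0639)/0.0533] = Φ(1.40) = 0.920.

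The stated 92% is reproduced for the test it names.

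**2. Surgical patients per coefficient.** 992/16 = 62 (1000/16 = 62.5). Box 1 lists 19 demographic, 29 clinical and 5 patient-reported covariates, 53 in all. Counting levels minus one for categorical items gives 28 + 46 + 5 = 79 coefficients, or 75 if the four missing-data levels are not modelled. The ratio is 62/79 = 0.78 to 62/75 = 0.83. This assumes linear terms and mutually exclusive categories. Removing BMI and metabolic syndrome, which are built from other listed items, leaves 73–77, or 62/77 = 0.81 to 62/73 = 0.85.

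**3. Effect on inference.** The SAP gives no weight variance, so this part rests on simulation. Assumptions: 992 patients, about 62 surgical, 79 coefficients, 6 true confounders, non-surgical PASS rate 0.60, confounder SD 0.9 on the outcome logit, and an outcome model with treatment and four strata (1000 runs per setting). Two covariate designs were used: (a) a mix shaped like Box 1, and (b) 79 independent normals. Effective size is (Σw)²/Σw² in the surgical arm.

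| Design, linear-predictor SD | Effective size | Null rejection, sandwich | Null rejection, model-based | Rejection at 0.80 vs 0.60, sandwich |
|---|---|---|---|---|
| (a) 0.5 | 16.2 | 13.2% | 40.2% | 50.1% |
| (a) 0.9 | 11.3 | 15.7% | 48.5% | 49.2% |
| (b) 0.5 | 16.3 | 10.5% | 35.1% | 50.4% |
| (b) 0.9 | 11.7 | 17.4% | 50.7% | 48.9% |

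A separately coded repeat with independent normals and no strata (300 runs per setting) gave 10–18% and 38–55%. With no confounding at all, overfitting alone cuts the effective size to about 19. In design (a), weighting brings the mean signed standardised difference on the confounders from 0.21 and 0.37 to 0.00. The mean absolute difference only falls from 0.22 to 0.19 and from 0.37 to 0.24, so random imbalance remains.

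**4. Bootstrap re-estimating the score** (design (a), 100 resamples). With the full list it rejected a true null in 0 of 400 runs. At 0.80 against 0.60, for the two SD settings, it rejected in 0/70 and 0/70 using the bootstrap SE, and in 4/70 and 10/70 using percentile limits. These are small runs: 10/70 has a 95% interval of roughly 7–25%.

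**5. Larger surgical counts.** Null rejection over all runs, sandwich then model-based: at 100, 5–9% and 25–41%; at 200, 4–7% and 12–28%.

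**6. Smaller models at 62.** With 12 terms including all 6 confounders, the effective size is 28–43, sandwich null rejection 4–7%, and rejection at 0.80 against 0.60 53–69%. Model-based null rejection is still 12–24%.

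**7. Power if weighting reduces surgical information.** Step 1 with the surgical number replaced by an effective size: 92% at 62, 85% at 49.6 (80%), 63% at 31 (50%), 40% at 18.6 (30%).

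**The case against.** Four objections have weight.

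- **The surgical count is not known.** 1:15 is an expectation, and the group sizes in Table 1 are blank because extraction follows publication of the SAP. This stands. With about 200 surgical patients a sandwich SE is close to nominal. A model-based SE is still too small, so the variance method must be named at any of these counts.
- **The magnitudes depend on assumptions.** This also stands. With stronger prediction of treatment, another simulation gave an effective size of 6–11 and sandwich rejection of 19–27%. The figures show direction and rough size and are not estimates for this cohort.
- **Wide adjustment is the point of an emulated trial.** The full list leaves a bias of only about 0.02–0.06 on the log odds ratio. Truncation, or a 12-term set missing 2 of the 6 confounders, leaves about 0.12–0.28, and that reduced set still has sandwich null rejection of 6–12%. The choice of a smaller model is therefore a trade-off. The requests for a named variance and weight diagnostics do not depend on it.
- **Some checks exist.** The standardised differences and the crude odds ratio would give a reader some warning. Both are descriptive and neither protects the weighted analysis.

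A reader might also infer that a too-narrow interval could produce a false finding of comparability under the 0.80–1.25 rule. The figures do not support that. The rule needs a log-odds-ratio interval narrower than ln(1.25/0.80) = 0.446. Unweighted, at a rate of 0.60, 62 against 930 gives 2×1.96×√[1/(62×0.24) + 1/(930×0.24)] = 1.05, and even 496 against 496 gives 0.51. The rule is practically out of reach at this sample size.

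**Conclusion.** The point holds as an under-specification of the primary analysis that matters at the SAP's own planning size. About 62 surgical patients against 75–79 coefficients follows from the document. So does the absence of a variance estimator and of any safeguard on the weights beyond stabilisation.

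It is tempting to say that the planned test rejects a true null well above 5%. The SAP does not support that, because it defines no single test. Under the stated assumptions, the full list at 62 gives about 10–18% with a sandwich SE, 35–55% with a model-based SE, and 0 of 400 with a bootstrap that re-estimates the score. The supportable conclusion is that error control is undetermined: inflated under the first two and very conservative under the third.

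The 92% is not a miscalculation. It describes an unweighted test that is not the main analysis. Since follow-up is complete, this is a secondary matter of disclosure.

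**What to change.** Amend the SAP before outcome data are analysed:

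1. State the actual number of surgical patients and the number of propensity parameters.
2. Name a robust (sandwich) variance or a bootstrap that re-estimates the propensity score, and rule out the model-based SE. With the full list at about 62 surgical patients neither is adequate alone, so this goes together with item 3.
3. Remove derived or redundant terms (BMI with height and weight; metabolic syndrome with its components). If surgical patients per parameter remain few, prespecify a smaller confounder set on clinical grounds, without reference to outcomes, and acknowledge the bias–variance trade-off. Diagnostic group and baseline Quick-DASH and VAS are not in the Box 1 covariate list, so using them would be an explicit addition.
4. Report post-weighting standardised differences, the weight distribution and the effective sample size, with a truncated-weight analysis as a sensitivity analysis.
5. State that 92% applies to the unweighted test, and give power over a range of effective surgical sizes, as in step 7 of the working.

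The cost is SAP wording and modest analysis work. The sample cannot change. The stated power will look less favourable, and a reduced set or truncation may leave some residual confounding.
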